8.3.1 Potential drug-induced liver injury

The number and percentage of study participants who meet one or more of the following potential drug-induced liver injury (pDILI) criteria during TE period will be summarized by entire study, actual treatment group at the time of meeting the following criteria and RLZ total:

- Participants with at least one post-Baseline liver laboratory assessment
- Incidence of potential hepatotoxicity with symptoms potentially associated with hepatitis or hypersensitivity
- Incidence of potential hepatotoxicity with no symptoms potentially associated with hepatitis or hypersensitivity
- Laboratory criteria for pDILI:
 - (AST or ALT $\geq 3 \times$ ULN) and TBL $\geq 1.5 \times$ ULN
 - (AST or ALT $\geq 3 \times$ ULN) and TBL $\geq 2 \times$ ULN
 - (AST or ALT $\geq 3 \times$ ULN) and TBL $\geq 2 \times$ ULN and ALP $< 2 \times$ ULN (Hy's Law)

In order to meet the above criteria, a study participant must experience the elevation in bilirubin and ALT or AST (and the absence of the ALP elevation) at the same visit. For example, a study participant who experiences a $\geq 2 \times$ ULN elevation of bilirubin at one visit and a $\geq 3 \times$ ULN elevation in ALT (or AST) at a subsequent visit has not fulfilled the Hy's law criteria. If participant meets part of one criterion but at least one parameter is unknown, then he/she should not be considered for meeting the criterion.

Additional analyses for liver function tests (LFTs) will be performed to assess the potential for liver toxicities in accordance with the United States Food and Drug Administration guidelines. Per guidelines, the following criteria will be used to define levels of LFT elevation:

- Aspartate aminotransferase (AST): $>3 \times$ ULN, $>5 \times$ ULN, $>8 \times$ ULN, $>10 \times$ ULN, $>20 \times$ ULN
- Alanine aminotransferase (ALT): $>3 \times$ ULN, $>5 \times$ ULN, $>8 \times$ ULN, $>10 \times$ ULN, $>20 \times$ ULN
- AST or ALT: $>3 \times$ ULN, $>5 \times$ ULN, $>8 \times$ ULN, $>10 \times$ ULN, $>20 \times$ ULN
- Total bilirubin (TBL): $>1.5 \times$ ULN, $>2 \times$ ULN
- Alkaline phosphatase (ALP) $>1.5 \times$ ULN

The number and percentage of study participants who meet one or more of the above LFT elevation criteria during TE period will be summarized by entire study, actual treatment group at the time of meeting the above criteria and RLZ total.

A listing will also be provided for study participants who meet at least one of the above criteria. All results obtained at that visit for the specified parameters will be displayed.

8.4 Vital signs, physical findings, and other observations related to safety

8.4.1 Vital signs

Observed values and changes from Baseline of vital signs variable (pulse rate, systolic and diastolic blood pressure, and temperature) will be summarized for each study cycle by actual dose received within the study cycle and RLZ total.

The number and percentage of participants who meet each of the markedly abnormal (MA) criteria outlined in [Section 13.6](#) during TE period will be summarized for entire study by the initial dose level and RLZ total, and for each study cycle by actual dose received within the study cycle and RLZ total at any visit (including unscheduled visit).

Additionally, the vital signs variables that are categorized as normal or TE MA based on the MA criteria will be presented in shift tables from Baseline to any post-Baseline visit (including unscheduled visit) for entire study by RLZ total only, and for each study cycle by actual dose received within the study cycle and RLZ total.

A by-participant listing of all vital sign measurements and change from Baseline will be presented by treatment group, study cycle, and visit. The listing will include a flag for values identified as MA. Unscheduled measurements will be presented in the listings.

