3.3 Definition of Baseline values

For the analyses done by entire study, Baseline values will be the last available value prior to or on the same date of first administration of IMP in MG0007. Scheduled or unscheduled measurements can be used as the Baseline value.

For the analyses done by study cycle, Baseline values will be defined as the last available value prior to or on the same date (and same time if time is collected for the individual assessment) of first administration of IMP at each cycle (ie Baseline [Day 1]) value for that cycle.

In case of baseline of specific cycle is missing, values from previous cycle or previous studies EOS visit will be considered as baseline for that cycle.

For [REDACTED] Baseline values will be the Baseline values determined in MG0003.

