Abbreviations: ALT = alanine aminotransferase; AST = aspartate aminotransferase; dL = deciliter; GGT: gamma glutamyltransferase; L = liter; mg = milligram; mmol = millimoles; μ g = microgram; U = unit; ULN = upper limit of normal

Note: Marked abnormality criteria are defined by Grade 3 or higher events according to the Common Terminology for Adverse Events (CTCAE), Version 5.0, November 17, 2017 unless otherwise noted.

¹eGFR is calculated using the Chronic Kidney Disease Epidemiology Collaboration or CKD-EPI formula (https://qxmd.com/calculate/calculator_251/egfr-using-ckd-epi) which is $eGFR = 141 * \min(Scr/\kappa, 1)^\alpha * \max(Scr/\kappa, 1)^{-1.209} * 0.993^{\text{Age}} * 1.018$ [if female]; where Scr is serum creatinine (mg/dL), κ is 0.7 for females and 0.9 for males, α is -0.329 for females and -0.411 for males, min indicates the minimum of Scr/ κ or 1, and max indicates the maximum of Scr/ κ or 1. For derivation from values in standard units (umol/L) the κ values are 61.88 for females and 79.56 for males.

²Includes CRP and High Sensitivity (HS) CRP. Reference for marked abnormality criteria: Nehringer, S.M.; Goyal, A.; Patel, B.C. (2020). StatPearls Publishing, web link: <https://www.ncbi.nlm.nih.gov/books/NBK441843/>. A moderate elevation of CRP level per referred reference is used for the marked abnormality criteria for RLZ to ensure a change suggestive of inflammatory process is captured. Standard CRP test should be used. In case high sensitivity CRP (hs-CRP) test have been used in any ongoing studies apply same value (>100 mg/L) as markedly abnormal criteria.

³Corrected Calcium (mmol/L) = $0.02 * (40 - \text{Albumin (g/L)}) + \text{Calcium (mmol/L)}$.

⁴Immunoglobulin G criterion based on immunodeficiency literature and noted in RLZ study protocols.

⁵Glucose high criterion defined by Grade 3 and higher events according to CTCAE, Version 4.03, June 14, 2010.

Table 13–9: Vital Signs

Parameter	Abnormality Criteria
Pulse Rate (beats/minute)	≤ 50 and a decrease from Baseline of ≥ 15 ≥ 120 and an increase from Baseline of ≥ 15
Systolic Blood Pressure (mmHg)	≤ 90 and a decrease from Baseline of ≥ 20 ≥ 180 and an increase from Baseline of ≥ 20
Diastolic Blood Pressure (mmHg)	≤ 50 and a decrease from Baseline of ≥ 15 ≥ 105 and an increase from Baseline of ≥ 15
Temperature	$>101^{\circ}\text{F}$ (38.3°C)
Body Weight	$\geq 10\%$ decrease from Baseline $\geq 10\%$ increase from Baseline

Table 13–10: Electrocardiogram

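### Vital-sign shift tables use a category that no Baseline pulse or blood pressure can meet, so every Baseline value reads normal and the tables repeat the incidence tables

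*SAP*

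**What the plan says.** SAP 8.4.1 plans four presentations of vital signs:

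- **Summaries** of observed values and changes for pulse, systolic and diastolic pressure and temperature, by cycle and dose.
- **Incidence tables**: "The number and percentage of participants who meet each of the markedly abnormal (MA) criteria outlined in" Section 13.6, during the TE period, for the entire study and by cycle.
- **Shift tables**: "the vital signs variables that are categorized as normal or TE MA based on the MA criteria will be presented in shift tables from Baseline", set against any later visit, for the entire study (all rozanolixizumab participants combined) and by cycle and dose.
- **A listing** of every measurement and change, with an MA flag.

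The criteria are in SAP Table 13-9. Pulse is low if "≤ 50 and a decrease from Baseline of ≥ 15". Systolic pressure is low if "≤ 90 and a decrease from Baseline of ≥ 20" and high if "≥ 180 and an increase from Baseline of ≥ 20". Diastolic pressure is high if "≥ 105 and an increase from Baseline of ≥ 15". High pulse (120, with a rise of 15) and low diastolic pressure (50, with a fall of 15) have the same two-part form. Temperature has an absolute limit only (above 38.3 C).

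For entire-study analyses, SAP 3.3 states that "Baseline values will be the last available value prior to or on the same date of first administration of IMP in MG0007". For by-cycle analyses the same rule is applied to the first dose of each cycle. SAP 8.4.1 gives no separate rule for classifying a Baseline value.

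**The concern.** A shift table cross-classifies a Baseline state against a later state, so the same category must be attainable at both times. Here the only abnormal category contains a change from Baseline, which a Baseline value cannot have. The Baseline side of the table then carries no information, a very high or very low starting value is printed as normal, and a return from an extreme value to an ordinary one does not show as a shift.

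This is not the SAP's general convention. The laboratory shift tables (SAP 8.3) use low, normal and high by reference range, and the ECG shift table (SAP 8.4.2) uses the investigator's interpretation. A Baseline value can fall in any of those categories.

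Vital-sign values and changes are a named safety endpoint in a study whose primary objective is safety, so the tables should be readable as labelled.

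**Working it through.** The plan gives no figure to reproduce here. The check applies its rules literally.

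**Rule.** With v the value, b the Baseline, and Table 13-9 supplying the limits L (low) and H (high) and the change d:

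MA if (v ≤ L and b − v ≥ d) or (v ≥ H and v − b ≥ d)

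| Variable | L | H | d |
|---|---|---|---|
| Pulse | 50 | 120 | 15 |
| Systolic | 90 | 180 | 20 |
| Diastolic | 50 | 105 | 15 |

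**Step 1: the Baseline value itself.** Put v = b. Both differences are 0, and 0 ≥ 15 and 0 ≥ 20 are false, so no Baseline value is MA. As a check, every whole number from 20 to 280 (261 values) was run against itself:

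| Variable | Values beyond an absolute limit | Values classed MA at Baseline |
|---|---|---|
| Pulse | 192 | 0 |
| Systolic | 172 | 0 |
| Diastolic | 207 | 0 |

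These are counts of tested numbers, not of participants. The documents give no Baseline vital-sign data, so the number of participants concerned is unknown.

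**Step 2: example records.**

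| Record | Change | Shift table as written | Absolute limits only |
|---|---|---|---|
| Systolic 185 to 195 | +10 | normal to normal | high to high |
| Systolic 185 to 130 | −55 | normal to normal | high to normal |
| Systolic 185 to 204 | +19 | normal to normal | high to high |
| Systolic 185 to 205 | +20 | normal to TE MA | high to high |
| Systolic 165 to 185 | +20 | normal to TE MA | normal to high |
| Diastolic 110 to 112 | +2 | normal to normal | high to high |
| Pulse 48 to 45 | −3 | normal to normal | low to low |
| Pulse 125 to 130 | +5 | normal to normal | high to high |

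**Step 3: by cycle.** Baseline is reset at each cycle. Suppose systolic pressure rises from 160 to 185 in cycle 1 (+25, TE MA), is 185 at the cycle 2 Baseline, and then reaches 195. The cycle 2 table shows normal to normal (+10). The entire-study table still flags the participant (195 − 160 = 35). A cycle 2 Baseline could be MA only if change were taken against the study Baseline, and SAP 3.3 does not do that for by-cycle analyses.

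**Step 4: overlap with the incidence tables.** If all participants with a Baseline value sit in one row, the remaining content is the split of that row into normal and TE MA after dosing, which is the incidence of TE MA. The shift table shows somewhat less than the incidence table. It pools high and low, while incidence is given for each criterion, and its entire-study version has no breakdown by initial dose.

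**Step 5: temperature.** A Baseline of 38.5 C exceeds 38.3 C and so meets the MA limit. The shift category, however, is TE MA. SAP 8.3 defines treatment-emergent as not present before the first dose of the cycle. Read literally, that label excludes a Baseline temperature too.

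**The case against.** The strongest reply is that little is lost, and most of it stands.

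- **Other outputs show the values.** A reader might infer that participants with extreme Baseline values are hidden. They are not. Observed values are summarised by cycle with minimum and maximum (SAP 3.1 and 8.4.1), and every measurement is listed.
- **The combined criterion is sensible for its main purpose.** Requiring a change separates on-treatment movement from pre-existing abnormality, and the incidence tables should keep it. A reader might also infer that someone starting at systolic 185 can never be flagged. Step 2 shows otherwise: 205 is flagged.
- **Temperature is not a clean exception.** It might seem to escape because its limit is absolute. That holds only if the TE label is ignored at Baseline.
- **An unseen document may help.** SAP Section 1 relies on a programme safety analysis plan, which might define the Baseline category. That cannot be checked here, and SAP 8.4.1 does not refer to it for this purpose.
- **The remedy has a cost.** With absolute limits alone, systolic 179 to 180 becomes a shift on 1 mmHg, and a Baseline of 179 is still called normal.

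None of this gives the Baseline side of the pulse and blood pressure tables any content.

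**Conclusion.** The point holds as a minor defect in a secondary safety display. For pulse, systolic and diastolic pressure, 100% of participants with a Baseline value fall in the normal row, in every by-cycle table and in the entire-study table, whatever the value. The tables therefore add nothing to the TE MA incidence tables, and they label values such as a Baseline systolic pressure of 185 as normal.

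This rests on reading SAP 8.4.1, Table 13-9 and SAP 3.3 as written, with no further Baseline rule in the programme plan.

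The documents do not support going further. The TE MA incidence counts, the MA flag, the observed-value summaries and the listing are all unaffected. The analyses are descriptive (SAP 4.1 and 4.6), and the documents tie no decision to these tables.

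**What to change.** Add a sentence to SAP 8.4.1. For the shift tables only, Baseline and post-Baseline values are classified by the absolute limits already in Table 13-9, without the change or treatment-emergent requirement:

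- pulse: low ≤50, high ≥120;
- systolic: low ≤90, high ≥180;
- diastolic: low ≤50, high ≥105;
- temperature: normal, or above 38.3 C.

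Keep the combined criterion for TE MA incidence and for the MA flag. Because the TE label also limits the post-Baseline side to 56 days after the cycle's last dose, state the intended window explicitly once the label is removed.

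Add a footnote that the shift categories differ from the TE MA flag, since a small change across a limit will now count as a shift.

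The alternative is to drop the shift tables for pulse and blood pressure as redundant.

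The first option costs a short text change and one reprogrammed category. The second removes outputs. Neither needs new data or new thresholds.

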8.4.2 Electrocardiograms

The following ECG variables will be reported:

- Heart rate
- PR interval
- RR interval
- QRS duration
- QT interval
- QT corrected for heart rate using Fridericia's formula ($QTcF = QT/RR^{1/3}$)

Observed values and changes from Baseline will be summarized for each study cycle by actual dose received within the study cycle and RLZ total, at scheduled visit and by ECG variable. The number and percentage of participants with normal, abnormal not clinically significant and abnormal clinically significant ECG results by investigator will be provided in a shift table from Baseline to worst post-Baseline interpretation for each study cycle by actual dose received within the study cycle and RLZ total and for entire study by RLZ total only.

For the ECG data, all calculations of changes from Baseline and descriptive statistics will be based on the mean of the triplicate assessments at each visit. In the event that there are not 3 available measurements at a given visit, the mean will be calculated based on the number of measurements for which data are provided.

The number and percentage of study participants who meet each of the MA criteria outlined in [Section 13.6](#) during TE period will be summarized for entire study by the initial dose level and RLZ total, and for each study cycle by actual dose received within the study cycle and RLZ total at any visit (including unscheduled visit).

A listing of electrocardiogram data will be presented, including repeated and unscheduled measurements.

[figure not shown]
8.4.3 Other safety endpoints

8.4.3.1 Physical examination

[figure not shown]
Results of abnormalities in physical examination are not collected in MG0007 therefore no listing or table will be provided for physical examination abnormal results.

8.4.3.2 Suicidal risk monitoring

Suicidal ideation is defined as an event in any of the following 5 categories:

Suicidal behavior is defined as an event in any of the following 5 categories:

Suicidal behavior or ideation is defined as an event in any of the above 10 categories.

Self-injurious behavior without suicidal intent is corresponding to the response to [REDACTED] in questionnaire.

A by-participant listing of the C-SSRS questionnaire data will be provided by treatment group and study cycle.

8.4.3.3 Assessment and management of Tuberculosis (TB)

By-participant listings of interferon gamma release assay (IGRA) TB test, chest X-ray and TB signs and symptoms questionnaire for TB will be provided.

9 EFFICACY ANALYSES

All efficacy analyses tables and figures will be performed based on the SS by study cycle and highest dose level received within the cycle and RLZ total as described in [Section 3.6](#). All listings will be presented using FAS. No statistical testing will be performed for efficacy analyses. All efficacy endpoints will be summarized descriptively, unless specified otherwise.

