9.2 General statistical considerations

Statistical evaluation will be performed by the Sponsor or designee and supervised by the Exploratory Statistics Department of UCB. For safety analyses, data will be summarized by dose levels of rozanolixizumab at the time of the event or measurement. For efficacy, data will be summarized by the dose first received in the study. Additionally, efficacy data will be summarized by dose levels of rozanolixizumab received in each treatment cycle.

All analyses will be performed using Statistical Analysis System (SAS[®]) version 9.3 or later (SAS Institute, Cary, NC, USA). Continuous variables will be summarized by visit (where applicable) with the statistics including the number of study participants (n), mean, standard deviation (SD), median, minimum, and maximum. Categorical variables will be summarized by visit (where applicable) with frequency counts and percentages.

If not otherwise stated, Baseline values will be the last available predose value, or in the case of analyses done by 6-week treatment cycle, Baseline will be defined as the Baseline (Day 1) value for that cycle. This will be clearly defined in the SAP. All relevant data will be listed by treatment group and study participant.

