9.4 Planned efficacy and other analyses

9.4.1 Efficacy analyses

The main efficacy endpoint is the "Change from Baseline (Day 1) to Day 43 in MG-ADL score," for each of the first three 6-week treatment cycles where the Baseline of the respective cycle will be used as reference.

The summaries will be provided overall and by randomized treatment in-line with a treatment policy approach. Observed results will be presented for the different cycles (1 to n) regardless of the first cycle being mandatory or not. Missing values will not be imputed. Further summaries will be presented by the treatment received in each cycle.

The other secondary efficacy endpoints, Change from Baseline (Day 1) to Day 43 in QMG score, Change from Baseline (Day 1) to Day 43 in MG-C score, Change from Baseline (Day 1) to Day 43 in MG Symptoms PRO 'Muscle Weakness Fatigability' score, Change from Baseline (Day 1) to Day 43 in MG Symptoms PRO 'Physical Fatigue' score, and Change from Baseline (Day 1) to Day 43 in MG Symptoms PRO 'Bulbar symptoms' score, will be analyzed in the same way as the main secondary endpoint based on the MG-ADL.

Time to MG-ADL response (≥ 2.0 -point improvement from Baseline [Day 1]) for each treatment cycle will be summarized using time-to-event methodology (Kaplan Meier).

The time between consecutive treatment cycles will be summarized in order to provide information on how long the effect of rozanolixizumab lasts, ie, how long it will take to introduce a new cycle.

The number and percentage of participants achieving Minimal Symptom Expression (MG-ADL score of 0 or 1) at any time during the Treatment and Observation Periods will be summarized by cycle and by dose administration in that cycle.

Additionally, the number of treatment cycles will be summarized by treatment group.

Further summaries will be described in the SAP.

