3 DATA ANALYSIS CONSIDERATIONS

3.1 General presentation of summaries and analyses

For safety analyses, data will be summarized by dose levels of rozanolixizumab at the time of the event or measurement. For efficacy analyses, data will be summarized by the dose first received in the study. Additionally, efficacy data will be summarized by dose levels of rozanolixizumab received in each treatment cycle.

Statistical analysis and generation of tables, figures, participant data listings, and statistical outputs will be performed using SAS® Version 9.3 or higher. All tables and listings will use Courier New font size 9.

Descriptive statistics will be displayed to provide an overview of the study results. For continuous variables, descriptive statistics will include number of participants with available measurements (n), mean, standard deviation (SD), median, minimum, and maximum.

For categorical variables, the number and percentage of participants in each category will be presented. Unless otherwise noted, the denominator for percentages will be based on the number of participants included in the respective analysis set. Participants with missing data can generally be accounted for using the following approaches:

- For summaries of demographics and Baseline characteristics: summarize percentages based on all participants in the analysis set and include a “Missing” category (corresponding to participants with missing data for the variable being summarized) as the last row in the list of categories being summarized.
- For summaries of efficacy and safety endpoints, unless otherwise specified: summarize percentages based only on those participants with observed data for the variable being summarized. As the denominator may be different from the number of participants in the

analysis set being considered, the denominator should be displayed in the table. The general format for displaying this will be “n/Nsub (%).”

Unless otherwise noted, all percentages will be displayed to one decimal place. No percentage will be displayed for zero counts, and no decimal will be presented when the percentage is 100%.

For the purpose of the tabulations the lower and upper confidence limits for the percentages will be truncated at 0 and 100% respectively.

For PK concentration data, summary statistics will include geometric mean, geometric coefficient of variation (geoCV), 95% confidence interval (CI) for geometric mean, arithmetic mean, SD, median, minimum, and maximum.

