3.6 Treatment assignment and treatment groups

For the analyses using SS, FAS and ES by entire study and first dose received, study participants will be grouped according to the highest dose levels of IMP participants received in MG0007 first cycle (7mg/kg or 10mg/kg). If participants switched dose in first cycle of MG0007, then they will be assigned to IMP 10mg/kg group. For example, if a participant's highest dose in first cycle of MG0007 is IMP 10 mg/kg and then changed to 7 mg/kg in the next cycle, then the participant will still be allocated to 10 mg/kg for these analyses.

For the safety analyses using SS by entire study and most recent dose received (summary of adverse events), participants will be grouped according to the most recent dose level of IMP participants received prior to the onset of AEs. For example, if a participant's last dose prior to an AE is 10 mg/kg, then the participant will be allocated to 10 mg/kg for this AE.

For the analyses performed using SS and FAS by treatment cycle, participants will be grouped according to the highest dose levels of IMP participants received (7mg/kg or 10mg/kg) within

each cycle. If participants switched dose within one cycle, then they will be assigned to IMP 10mg/kg group for that cycle. For example, if for a participant, the highest does in first cycle is 10 mg/kg and the highest dose received in second cycle is 7 mg/kg, then the participant will be allocated to IMP 10 mg/kg and 7mg/kg respectively.

For participants who were not treated in FAS and ES, they will be assigned to 'Not Treated' group.

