3.9 Changes to protocol-defined analyses

In the protocol section 9.2.1, the intercurrent events to be considered are the use of rescue therapy prior to Day 43 and permanent treatment discontinuation (or withdrawal from study) due to TEAEs. In the SAP, we consider use of rescue therapy prior to Day 43 and permanent treatment discontinuation due to TEAEs as intercurrent events.

In the protocol, the treatment policy strategy is described for the analysis meaning that all data was planned to be analyzed regardless of study participants receiving treatment with rescue therapy. Summaries will also be presented for the efficacy endpoints where participants will be censored at the time that they take rescue medication. In the SAP, time to MG-ADL response will be analyzed censoring the data at the time of the use of rescue therapy and all other efficacy endpoints will be summarized following treatment policy.

Protocol amendment 3 did not mention how to treat IgG when participants receive rescue therapy. In the SAP, the IgG values up to and including 8 weeks after start date of rescue therapy will be excluded from the analysis.

In the protocol section 8.3.1, Hy's law is defined as $>3 \times \text{ULN}$ ALT or AST with coexisting $>2 \times \text{ULN}$ total bilirubin in the absence of $<2 \times \text{ULN}$ ALP, with no alternative explanation for the biochemical abnormality (ie, without waiting for any additional etiologic investigations to have been concluded). In this SAP, Hy's law is defined as (AST or ALT $\geq 3 \times \text{ULN}$) and TBL $\geq 2 \times \text{ULN}$ and ALP $< 2 \times \text{ULN}$ to be consistent with Rozanolixizumab program SAP.

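### SAP section 9 groups every efficacy table by dose received in the cycle, so the randomised-dose and first-dose summaries set by the protocol and SAP 3.1 are not produced, and SAP 3.9 does not declare this

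*SAP*

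**What the plan says.** Protocol 9.4.1 covers the main efficacy endpoint, change in MG-ADL to Day 43 in each of the first three cycles: "The summaries will be provided overall and by randomized treatment in-line with a treatment policy approach". It then adds: "Further summaries will be presented by the treatment received in each cycle". The other change-from-Baseline secondary endpoints are to be handled the same way.

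Protocol 9.2 sets a general rule: "For efficacy, data will be summarized by the dose first received in the study", followed by "Additionally, efficacy data will be summarized by dose levels of rozanolixizumab received in each treatment cycle". SAP 3.1 repeats it: "For efficacy analyses, data will be summarized by the dose first received in the study", again with dose per cycle as the addition. SAP 3.6 defines the group needed: "For the analyses using SS, FAS and ES by entire study and first dose received, study participants will be grouped" by the highest dose received in the first MG0007 cycle.

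SAP section 9 then says: "All efficacy analyses tables and figures will be performed based on the SS by study cycle and highest dose level received within the cycle". SAP 3.9, which lists departures from the protocol, covers intercurrent events, rescue censoring, IgG after rescue and Hy's law. On efficacy it ends with "all other efficacy endpoints will be summarized following treatment policy" and says nothing about dose grouping.

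**The concern.** Three places make the dose a participant started on the leading efficacy grouping and dose per cycle the supplement. SAP section 9 keeps only the supplement. Two faults follow. The randomised-dose summary in protocol 9.4.1 is absent without being declared. On first dose, the SAP contradicts itself.

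The grouping matters because dose is fixed by assignment only in the first cycle. MG0003 entrants are randomised 1:1, and MG0004 entrants carry over their last dose (protocol 6.3). After that the Investigator may change the dose at the start of each cycle (protocol 4.1 and 9.2.1), and protocol 6.6 names drug-related adverse events as a reason for moving from 10 to 7 mg/kg. Two of the three cycles in the secondary endpoints are therefore open to switching. If the people who switch differ in how well they respond, the received-dose columns will differ even when the doses do not.

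**Working it through.** **Text check.** SAP 9.1 to 9.10 and 9.12 group by dose received within the cycle. Sections 9.2 and 9.3 say within study, apparently with the word cycle missing. The plots refer to treatment group, which the opening sentence of section 9 ties to dose within the cycle. The weight-tier tables use the administered dose in mg. Section 9.11 groups by dose in the *proceeding* cycle. None of the 12 subsections specifies randomised, planned or first dose. First or initial dose is used elsewhere: exposure (8.1), entire-study markedly abnormal results (8.3, 8.4) and time to first rescue (11.3). The gap is therefore in efficacy, not in the whole SAP.

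**Cycle 1.** SAP 3.6 uses the same rule, highest dose in that cycle, for the first-dose group and the by-cycle group. The cycle 1 columns are identical either way.

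**Cycle 2, illustrative size.** There is no plan figure to reproduce, and every input below is assumed. Half the participants start on each dose and there is no dose effect. The person-mean change is normal with mean −3 and between-person SD *S* = 1 or 2, and the within-person SD is 2. A negative change is improvement. The difference is the 10 mg/kg column minus the 7 mg/kg column.

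*(a) Reductions related to adverse events.* A fraction *d* of the 10 mg/kg group moves to 7 mg/kg. Adverse-event propensity has correlation *ρ* with the person mean. With *z* the upper-*d* normal quantile and *φ* the normal density, the movers differ from average by *m* = *ρSφ(z)/d*. The 10 mg/kg column shifts by −*md*/(1−*d*) and the 7 mg/kg column by *md*/(1+*d*), so

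difference = −2*ρSφ(z)*/(1−*d*²).

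Example: *d* = 0.10, *φ(z)* = 0.1755, *ρ* = 0.3, *S* = 1 gives −2 × 0.3 × 0.1755/0.99 = −0.11.

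| *d* | *S* = 1 | *S* = 2 |
|---|---|---|
| 0.10 | −0.11 | −0.21 |
| 0.20 | −0.17 | −0.35 |
| 0.30 | −0.23 | −0.46 |

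With *ρ* = −0.3 the signs reverse. With *ρ* = 0 the difference is 0.

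*(b) Increases in poor responders.* People on 7 mg/kg whose cycle 1 change is worse than −2 move up with probability *u*, and a random 15% of the 10 mg/kg group moves down. Let *p* be the proportion of poor responders, *f* = *up*, and *m* their excess in person mean. For *S* = 1, *p* = 0.327 and *m* = 0.493. For *S* = 2, *p* = 0.362 and *m* = 1.465. Then

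difference = *fm*[1/(0.85+*f*) + 1/(1.15−*f*)].

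| *u* | *S* = 1 | *S* = 2 |
|---|---|---|
| 0.05 | 0.02 | 0.05 |
| 0.10 | 0.03 | 0.11 |
| 0.25 | 0.08 | 0.27 |
| 0.50 | 0.16 | 0.53 |

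Simulation of the same model agrees to within 0.01 points. For responders (improvement of at least 2 points) it gives differences of 1.7 to 6.2 percentage points under (a) and 0.2 to 7.6 under (b). Grouped by original dose, the difference is within 0.01 points in every run.

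**Scale.** The total SD is √(1+4) = 2.24 or √(4+4) = 2.83. For 100 versus 100 the standard error is SD × √(2/100), which is 0.32 or 0.40.

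**The case against.** The strongest reply is that this is a documentation slip with little effect. SAP 3.1 still commits to first dose and 3.6 defines it, so section 9 merely fails to repeat it. The protocol itself uses two labels, first dose in 9.2 and randomised treatment in 9.4.1. The second cannot cover MG0004 entrants, who are not re-randomised. Since dose may not change within a cycle, first dose and randomised or planned dose should normally be the same, so the two faults are close to one. There is no testing, efficacy is secondary, the RLZ total column is untouched by switching, and SAP 8.1 reports treatment sequences.

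Most of that is fair. It limits the consequence but does not remove the conflict. The opening sentence of section 9 covers all tables and figures, so a programmer following it would not produce the summary in 3.1. If randomised dose was dropped on purpose, SAP 3.9 should say so. The two labels can be met by one grouping, because protocol 9.1 and SAP 3.5.2 already define a planned dose for MG0004 entrants.

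Two limits on the numbers also stand. Only two of the 14 non-zero values exceed the matching standard error (0.46 and 0.53 against 0.40), and both need strong switching with *S* = 2. The near-zero result by original dose holds by construction, because the model has no dose effect and sends everyone into cycle 2. Real cycle 2 and 3 tables include only people re-treated after worsening, so original-dose columns there are not clean randomised comparisons either. Re-treatment also makes 100 per column optimistic, given about 200 participants in total.

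**Conclusion.** The concern holds. SAP section 9 omits the protocol 9.4.1 summary by randomised dose without declaring it in SAP 3.9, and it contradicts SAP 3.1 and 3.6 on first dose. Nothing is lost in cycle 1 relative to first dose. From cycle 2, no planned score, responder or minimal-symptom table keeps the original assignment. The size cannot be derived from the documents. On the assumptions above it runs from nil, when switching is unrelated to response, to about half an MG-ADL point in an extreme case, and under adverse-event switching it can go in either direction. No type I error or power is involved. What is at stake is how readers interpret 7 and 10 mg/kg columns placed side by side. The change should be made, but the point does not threaten the study's primary safety objective.

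**What to change.** In SAP section 9, for the secondary efficacy endpoints in cycles 1 to 3, add summaries by original dose: the randomised dose for MG0003 entrants and the planned dose (last assigned in MG0004) for MG0004 entrants, kept whatever dose is given later. Keep the received-dose tables as the further summary and label them non-randomised from cycle 2. Footnote all cycle 2 and 3 tables as conditional on re-treatment after worsening. Align section 9 with SAP 3.1 and 3.6 and with protocol 9.2 and 9.4.1, stating how the protocol's two labels are reconciled. Record any remaining departure in SAP 3.9. Separate columns for MG0003 and MG0004 entrants are optional.

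The cost is SAP wording and repeat runs of existing table programs, since first-cycle or initial dose is already a grouping in SAP 8.1, 8.3 and 11.3. The drawback is more tables. No data collection or dosing rule changes.
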